 - b. Participants would be required to speak with a study clinician for evaluation and appropriate course of action, and encouraged to contact their personal therapist, if they have one.
 - c. Participants would be provided with a list of mental health resources.
 - d. If revealed prior to enrollment, these participants may not be enrolled according to the Exclusion criteria based on the clinical judgment of the CI.
 - e. If this finding is treatment-emergent, the participant may be removed from participation in the study based on clinical judgement of the CI or qualified designee. If these events emerge after enrollment and are clinically significant, they will be collected on the Adverse Events page. The participant's continuing eligibility will be assessed by the CI and the Medical Monitor.
 - f. Unless the steps above result in the participant leaving for psychiatric care right away or the clinician advises otherwise, the visit would be continued.
 - g. If it is determined that the participant is at imminent risk of suicide, the CI or CI-designated staff member will do one of the following: 1) Escort the participant to the Emergency Department; 2) Escort the participant to an appropriate mental health services facility (e.g. hospital psychiatric unit); or 3) call 911 and ensure that the participant is transferred to the responding medical personnel.
2. If the subject has suicidal ideation, and a plan to commit suicide (Suicidal Ideation Score = 5), the clinician administering the CSSRS will assess whether the risk is imminent. A score of 5 does not necessarily indicate an immediate risk if the thoughts are fleeting, fairly easily controlled, and deterrents are strong. If there is no imminent risk, the clinician will follow the procedure described in number 1. If there is imminent risk of suicidal behavior, the CI will:

- a. Call the National Suicide Prevention Lifeline at [name] immediately.
- b. Participants would be required to speak with a study clinician for evaluation and appropriate course of action, and encouraged to contact their personal therapist, if they have one, prior to leaving the laboratory.
- c. If it is determined that the participant is at imminent risk of suicide, the CI or CI-designated staff member will do one of the following: 1) Escort the participant to the Emergency Department; 2) Escort the participant to an appropriate mental health services facility (e.g. hospital psychiatric unit); or 3) call 911 and ensure that the participant is transferred to the responding medical personnel.
- d. If the participant will not comply and wishes to leave without consultation, call 911. Explain that the participant is in immediate danger of committing suicide. Provide a complete description of the participant and give any other needed details to ensure the subject's safety.
- e. Provide the subject with a list of mental health resources.
- f. Notify the study team as soon as possible. This includes all site staff and all study team members representing the Sponsor.
- g. If revealed during screening, these participants would not be enrolled according to the Exclusion criteria.
- h. If this finding is treatment-emergent, the participant may be removed from participation in the study based on clinical judgment of the CI or qualified designee. If these events emerge after enrollment and are clinically significant, they will be collected on the Adverse Events page. The participant's continuing eligibility will be assessed by the CI and the Medical Monitor.

The CIs will address a number of risks by enrolling participants without contraindicating conditions, including psychotic disorders and major medical conditions affecting the heart or lungs. Participants who pose a major suicide risk will not be enrolled in the study. Risks posed by cessation of marijuana use will be reduced by requiring a period of abstinence from marijuana upon the start of screening. Participants using marijuana before entering the study are required to abstain from use for two weeks before receiving study marijuana. Any participant that the CI or Medical Monitor believes has contraindicating history of, or current, moderate to severe substance use disorder will not be enrolled.

Untoward psychological reactions to marijuana will be dealt with by preparing participants for the subjective effects of the substance, and through first smoking marijuana in the presence of site staff during two introductory sessions. During this time, site staff will be able to help address any anxiety or paranoid feelings that may arise.

Participants will be informed of the effects that marijuana might have on driving and they will be advised to avoid driving immediately after use by seeking a designated driver and

by waiting a minimum of three hours after use prior to driving a motor vehicle. Participants will arrange rides home after each introductory session, and if they are unable to do so, the CIs will assist them in locating a ride from the study site.

Potential reproductive risks will be mitigated by restricting enrollment to women who are not pregnant or lactating, and by requiring that women of childbearing potential use an effective form of birth control and weekly pregnancy testing.

All study participants will be issued a study participant identification card (e.g. “wallet card”) stating that they may test positive for drugs of abuse as a result of being a research participant, listing the number of a 24-hour hotline, and containing contact information for the CI, identifying the sponsor and the relevant IRB, and the study National Clinical Trial Registry (NCT) number. The CIs will remind participants that they may still be cited or face penalties for erratic driving and the card will not mitigate this.

The CIs will address risks to confidentiality arising from the existence of digital video recordings of participant marijuana use by instructing participants to store their cameras securely in the lockbox provided to them as part of the study and informing them of the risks of exposing their personal video data to the internet. If a study computer tablet is lost or stolen, the study team will remotely delete files from the device, notify local police in the case of theft, and make every attempt to recover the unit. All tablets will be password protected and encrypted to minimize the likelihood that misplaced units will result in breach of confidentiality. Given the safeguards in place, breach of confidentiality from the tablet computer is unlikely as long as participants follow instructions for use and storage. All participant PHI will be stored in locked files or on secure computer servers, and managed in accordance with patient confidentiality procedures pertaining to electronic systems.

The CIs will discuss with participants the perceived stigma they ascribe to marijuana use and to consider the degree to which friends, family or other people within the community might respond if they observe or learn about the participant’s marijuana use.

This study involves take-home doses of study marijuana. To discourage the risk of diversion of unused marijuana during Stages 1 and 2, participants can choose to receive the amount of unused marijuana returned during Stage 1 or Stage 2 in Stage 3.

7.4 Medical Emergencies

If a participant experiences a medical emergency during the introductory sessions, the CI will be on call to determine course of action. If a participant experiences a medical emergency during the self-administration period at a location other than the study site, he or she will be directed to call 911 and inform the CI upon stabilization.

In the event of a psychological crisis arising during the study, participants and their community observers will be instructed to call the Participant Hotline as soon as possible. This call will be routed to the CI if it is confirmed that there is indeed a crisis. The CI, or

qualified designee if the CI is unavailable, will be on call at all times to receive information from the Participant Hotline.

Upon learning about the psychological crisis, the CI will assess the AE by:

- Obtaining a detailed history of the event over the phone
- Collecting information on any concomitant medications
- Verifying the above with the community observer if necessary
- Assessing expectedness, seriousness, severity, and relation to study drug
- All AEs will be assessed regardless of whether they occurred prior to or after self-administration.
- If the participant requires immediate care, they will be referred to the Emergency Department of the closest hospital.

The Mobile Crisis Response Team (if applicable), Emergency Department, Hospital, or Primary Care Provider, or the CI may prescribe medications or take steps to stabilize the participant experiencing an AE.

While participants are participating in Stage 1 of the study, which includes a placebo group, results of the THC drug test could break the study blind for a participant. During any discussion with a provider about how to treat a medical event, the CIs or site staff may need to inform the provider of the participant's medical history and course of treatment in the study. The CIs or site staff should inform the provider of the likelihood that the participant will test positive for marijuana, and determine with the provider if the study blind must be broken in order to effectively treat the participant. The CIs should discuss delaying routine drug screens administered during treatment unless it is medically necessary.

Regardless of condition assignment, all necessary steps will be taken to ensure participants receive whatever medical care is necessary for an AE. If an outside treatment provider informs the participant of the results of a drug test for marijuana during Stage 1 of a participant's study visits, the participant must be withdrawn from the study in order to protect the study blind.

8.0 Adverse Events

An AE is defined as any untoward or unfavorable medical occurrence in a clinical research study participant, including any abnormal sign (e.g. abnormal physical exam or laboratory finding), symptom, or disease, temporally associated with the participants' involvement in the research, whether or not considered related to participation in the research. This definition includes concurrent illnesses or injuries and exacerbation of pre-existing conditions.

An unexpected AE is one that is not listed in the current Investigator's Brochure or an event that is by nature more specific or more severe than a listed event.

All AEs will be monitored by the CI or site staff until resolution or, if the AE becomes chronic, a cause identified. If an AE is unresolved at the conclusion of the protocol, a clinical assessment will be made by the CI and/or Medical Monitor as to whether continued follow-up of the AE is warranted.

The severity of events reported on the AE CRF will be determined by the CI as:

- Mild: no limitation in normal daily activity
- Moderate: some limitation in normal daily activity
- Severe: unable to perform normal daily activity

The relationship of the study treatment to an AE will be determined by the CI, based on the following definitions:

1. Not Related

The AE is not related if exposure to the investigational product has not occurred, or the occurrence of the AE is not reasonably related in time, or the AE is considered unlikely to be related to use of the investigational product, i.e. there are no facts (evidence) or arguments to suggest a causal relationship, or the AE is more likely related to the participant's pre-existing condition.

2. Possibly Related

The administration of the investigational product and the AE are considered reasonably related in time and the AE could be explained by causes other than exposure to the investigational product.

3. Probably Related

Exposure to the investigational product and AE are reasonably related in time and the investigational product is more likely than other causes to be responsible for the AE, or is the most likely cause of the AE.

The relationship of the study treatment to an AE will be determined by the CI based on the assessment of the participants' report of symptoms.

8.1 Spontaneously Reported Reactions

Common expected AEs, that have been compiled from the literature on smoked marijuana reported in studies of human volunteers, are referred to as "spontaneously reported reactions" are: altered time perception, anxiety, difficulty concentrating, difficulty remembering things, dry mouth, feeling intoxicated (as drug effect, feeling high), feeling of heart racing/ or pounding in chest, feeling hungry, perceptual alteration (as enhanced sensation), sedation and feeling stimulated [107, 171]. Some participants may report feelings of paranoia or unusual thoughts [65]. AEs that are included in the

spontaneously reported reactions list will be separated in data analysis for review of expected vs. unexpected AEs.

8.2 Serious Adverse Events

The Site CI or qualified designee is responsible for determining if an AE is serious or non-serious. An SAE is defined as any untoward medical occurrence that at any dose:

- Results in death
- Is life-threatening (i.e., the participant was, in the opinion of the investigator, at immediate risk of death from the event as it occurred); it does not refer to an event which hypothetically might have caused death if it were more severe
- Requires or prolongs inpatient hospitalization
- Results in persistent or significant disability/incapacity (i.e., the event causes a substantial disruption of a person's ability to conduct normal life functions)
- Results in a congenital anomaly/birth defect
- Requires intervention to prevent permanent impairment or damage
- Is an important and significant medical event that may not be immediately life-threatening or resulting in death or hospitalization, but based upon appropriate medical judgment, may jeopardize the patient/participant or may require intervention to prevent one of the other outcomes listed above

AEs which do not fall into these categories are defined as non-serious. It should be noted that a severe AE need not be serious in nature and that a SAE need not, by definition, be severe.

In addition, a pre-existing event or condition that results in hospitalization should be recorded in the medical history. The hospitalization would not result in the event or condition being reported as a study-related SAE unless, in the view of the investigator, hospitalization was prolonged as a result of participation in the clinical trial or was necessary due to a worsening of the pre-existing condition. This is because the onset of the event (the reason for the procedure) occurred before the participant was entered into the trial. Hospitalization for cosmetic procedures, non-emergency prophylaxis, or abortion does not result in an SAE report unless, in the view of the investigator, hospitalization for these procedures was prolonged as a result of participation in the clinical trial.

8.3 Adverse Event Collection

AEs that will be collected during the protocol:

- SAEs will be collected through termination.
- All AEs will be collected from enrollment until end of the active study period (e.g. end of Cessation 2 or Stage 3, as applicable)
- Events requiring medical attention will be collected during the follow-up period through the participant's last six-month follow-up.
- Events related to planned treatments or physician visits for baseline conditions collected in the Medical History will not be collected unless there is an exacerbation of the condition.
- Any AE leading to withdrawal from the protocol will be collected throughout the study.
- All AEs related to changes in psychiatric status will be collected throughout the study.

AEs will be collected during introductory sessions and throughout Stage 1, Stage 2, and Stage 3, as well as associated cessation periods, on the Daily Diary. Information needed to determine severity and relatedness will be collected and confirmed by telephone contact conducted according to the Time & Events table. Each reported AE will be actively followed during follow-up phone calls or weekly visits until resolution. AEs will be recorded in the respective AE log eCRF based on onset date, e.g. an AE reported during Introductory Session 1 or the Stage 1 self-administration period would be recorded on the Stage 1 AE log eCRF. CIs or qualified site staff are responsible for review of safety data.

A Memory Aid Card will be provided to the subject on the last visit prior to the six-month follow-up to record information on medications taken to treat SAEs, AEs leading to withdrawal and psychiatric AEs during the follow-up period between the end of self-administration and the six-month follow-up evaluation. The Memory Aid Card will not be collected, but information from the card will be used to aid the participants in providing information to site staff. This information may be collected by phone.

8.4 Adverse Event Reporting

All SAEs which occur during the course of the trial, whether considered to be associated with the study drug or not, must be reported to the sponsor within 24 hours, or at the

latest on the following working day, of the site CI learning that an event occurred, irrespective of causality:

- Contact information for the MAPS Medical Monitors and Study monitor are provided in a separate document.
- All SAEs are to be assessed regardless of whether they occurred after drug administration, comparator product, placebo, or no treatment.
- SAEs will be assessed by the site CI and Sponsor Medical Monitor(s) for relatedness, seriousness, and unexpectedness and reported regulatory agencies, IRBs and CIs according to applicable regulations and policies.
- CIs should notify their respective IRBs according to IRB-specific timelines promptly after assessment and communication with the sponsor.
- SAE reporting to competent authorities is done by an authorized delegate of MAPS.

The Medical Monitor(s) will provide the required medical expertise in conjunction with site medical personnel to address trial-related medical questions or problems. In this capacity, the Medical Monitor(s) are responsible for the overall safety of the participants, the ongoing safety evaluation of the investigational product and the notification of all concerned investigators/institutions of findings that could adversely affect the safety of participants.

The site CIs will communicate as needed with the Medical Monitors and study monitor to determine if the SAE is subject to expedited reporting and what follow-up information is needed for evaluation. If no consensus can be reached, the different assessments and the reasons for this must be summarized in writing. In any case the most conservative assessment drives the reporting procedure. The time frames for reporting SAEs to regulatory authorities begins when the sponsor has “initial information” of the event regardless of the form that initial notification takes. Expedited timelines will be followed according to regulatory, institutional, and IRB requirements.

The blind may be broken for an individual participant if there is an AE or other emergency requiring knowledge of the participant's condition assignment. This emergency unblinding would require approval from the site CI and Coordinating Investigator. For this purpose, the Randomization Monitor will provide dose assignment through the electronic randomization system.

The Sponsor will collaborate with investigators to ensure that all reports are submitted to the appropriate agency and IRB/EC within the required time frame and that they contain accurate and current information. The sponsor is responsible for ongoing safety evaluation of the investigational product and for the prompt notification of investigators conducting a MAPS-sponsored study and regulatory authorities of findings that could adversely affect the safety of participants, impact the conduct of the trial, or alter the IRB's approval/favorable opinion to continue the trial.

Such information may be distributed to investigators by means of periodically revised investigator brochures, reprints or published studies, reports or letters to clinical investigators, or other appropriate means. Any employee, contractor, or contract organization working on behalf of MAPS who discovers a serious adverse experience in the context of a clinical trial is responsible for alerting clinical trial staff. MAPS is responsible for collecting serious adverse experience information, submitting safety reports to regulatory agencies, and notifying investigators of safety issues.

9.0 Collection of Concomitant Medications and Therapies

Information about all concomitant prescription medications, and only over the counter (OTC) medications associated with an AE, will be collected from screening up to the day of the final study visit in Cessation 2 or Stage 3, as applicable, including reasons for use, date started, date ended and dose information if available. During the follow-up period after this visit and before the six-month follow-up, information on new psychiatric medications will be gathered on the day of the six-month follow up study visit. During the follow-up period, healthcare utilization associated with AEs requiring medical attention and psychiatric AEs will be collected. Medications recorded per protocol, including medications taken to treat AEs, will be recorded on a concomitant medications form eCRF. Information on participation in evidence-based psychotherapy for PTSD will be collected throughout the study. Therapies and healthcare utilization recorded per protocol will be recorded on a concomitant therapies form eCRF.

10.0 Laboratory Assessments

10.1 Clinical Laboratory Assessments

The CI or qualified study personnel at each site will examine laboratory assessments gathered at screening, for assessing participant eligibility. The CIs will use a list of normal ranges to conclude whether participants are eligible for the protocol, and will indicate justification for admitting participants with abnormal values.

The following laboratory assessments will be performed as specified in the Time and Events table.

Serum electrolytes and the metabolic profile, which includes:

- ALT/SGPT
- Albumin:globulin (A:G) ratio
- Albumin, serum
- Alkaline phosphatase, serum
- AST/SGOT
- Bilirubin, total
- BUN
- BUN:creatinine ratio
- Calcium, serum
- Carbon dioxide
- Chloride, serum
- Creatinine, serum
- Globulin, total
- Glucose, serum
- Potassium, serum
- Protein, total, serum
- Sodium, serum

CBC, which includes:

- Hematocrit
- Hemoglobin
- MCV
- MCH
- MCHC
- RDW
- Percentage and absolute differential counts
- RBC
- WBC

Urinalysis, which includes:

- Color
- Appearance
- Specific gravity
- pH
- Protein
- Glucose
- Ketones
- Occult blood
- Leukocyte esterase
- Nitrite
- Bilirubin
- Urobilinogen

Participants who test positive on the qualitative urine drug test at both pre and post cessation timepoints will have a Quantitative Urine THC-COOH Drug Test to determine likelihood of compliance with abstinence requirements. Quantitative testing will be conducted by Dominion Diagnostics using GC/MS testing methods. An algorithm developed by Huestis and colleagues will then be used to determine the confidence that a participant completely abstained from cannabis during each 2-week cessation period. Participants for which samples indicate 90% or greater confidence will be considered compliant. Participants who provide samples that indicate 80-90% confidence will have blood samples tested for additional information in order to determine compliance. Samples with < 80% confidence will be considered non-compliant. Non-compliance will be evaluated and handled by study investigators on a case-by-case basis with regards to study continuation and utilization of data.

Thyroid function, which includes:

- TSH high sensitivity

A urine-dip pregnancy test for participants of childbearing potential will be performed as specified in the Time & Events table.

A qualitative urine drug screen will be administered at Screen 1 and 2. A qualitative urine drug screen will be administered throughout the study at the study sites according to the Time & Events table.

An 80-hour ETG urine dip test to test for recent alcohol consumption will be performed at the study sites according to the Time & Events table.

Clinical laboratory assessments will be drawn at the site or closest available LabCorp facility. These samples will be processed at LabCorp.

For the Arizona site:

[name]
[name]

For the Maryland site:

[name]
[name]

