5.3 Removal of Enrolled Participants from the Study

Participants can withdraw consent at any time without prejudice. The CI can withdraw a participant if, in his or her clinical judgment, it is in the best interest of the participant or if the participant cannot comply with the experimental procedures and related visits that are critical for safety, and this will be recorded in the participant's source records and CRF. Participants who are not able to comply with required periods of abstinence from marijuana use will be withdrawn from treatment. If the CI withdraws a participant from treatment, the CI will explain the reason for withdrawing to the participant, and refer them to standard clinical care for PTSD. Participants who are withdrawn will not be denied care within or outside of the VA or participating institutions. Participants will be clinically monitored after withdrawal by the CI. Whenever possible, the tests and evaluations listed for the termination and outcome visits will be carried out. Efforts will be made to obtain information about AE resolutions, if applicable. All participants who sign informed consent, meet study eligibility criteria including 2 weeks abstinence period prior to randomization, and who receive initial dose of study medication will be included in intent to treat analyses (including data/outcome data for study participants who withdraw consent up to the time consent is withdrawn).

Participants who discontinue treatment during the study will not be replaced. Recruitment and enrollment will continue until 76 participants have completed the Primary Endpoint.

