12.0 Data Analysis

Key Personnel, MAPS, and the biostatistician will agree on a detailed Statistical Analysis Plan prior to the beginning of recruitment. The biostatistician will perform an "intent to treat" (ITT) analysis using repeated measures analysis of covariance (ANCOVA) to compare demographics. Distribution of treatment dropouts will be examined by condition and if found to be unequal, the sponsor will control for group assignment in the ITT analysis.

Primary analysis of observer-blind CAPS-5 data collected at Baseline and end of Stage 1 will be conducted using ANCOVA with marijuana concentration as a between-subject factor and time of assessment as a within-group factor. If effects of marijuana concentration are detected at Stage 1, a similar secondary analysis will also be performed with Stage 2 data using Stage 1 data as a covariate for each outcome measure. Effect size will be estimated based on all outcome measures using Cohen's techniques. The biostatistician will conduct secondary exploratory analyses of weekly assessments of PCL-5, ISI, IDAS, IPF, WBR, CSSRS, MWC, CUDIT-R, DEQ and ACT scores using repeated measures ANCOVA or generalized linear mixed modeling, as described in the Statistical Analysis Plan. Statistical significance ($p < .05$) will be determined for all tests. All available data from repeated outcome assessments of all participants who are randomized, even if they withdraw from the allocated treatment prior to the primary endpoints, will be included in ITT analysis.

A repeated measures ANCOVA comparison of ratings on the DEQ and pulse will be conducted, with marijuana condition as the main factor in the analysis. If a main effect of marijuana concentration is observed then pairwise comparisons will be conducted to detect differences between each marijuana concentration.

Secondary exploratory analyses will be conducted examining weekly assessments of self-reported (via the ISI) and objective (via Actigraphy) measures of sleep. Independent repeated measures ANCOVAs will be conducted. In terms of self-reported sleep, weekly total scores from the ISI will be entered as the repeated measure with group entered as the IV. In terms of objective sleep (via Actigraphy) repeated measures ANCOVAs will be conducted with weekly total sleep time (TST), wake after sleep onset (WASO), sleep

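### Section 10.1 lets study investigators decide case by case whether data are used after failed abstinence, which conflicts with the ITT rules in 5.3 and 12.0

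*Protocol*

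**What the plan says.** Section 10.1 sets out a laboratory rule for abstinence. Its purpose is to "determine the confidence that a participant completely abstained from cannabis during each 2-week cessation period". The entry condition is that "Participants who test positive on the qualitative urine drug test at both pre and post cessation timepoints will have a Quantitative Urine THC-COOH Drug Test". Confidence of 90% or more counts as compliant, 80-90% goes to blood testing, and "Samples with < 80% confidence will be considered non-compliant". The rule then ends: "Non-compliance will be evaluated and handled by study investigators on a case-by-case basis with regards to study continuation and utilization of data".

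Section 12.0 defines the ITT data differently: "All available data from repeated outcome assessments of all participants who are randomized" are to be used, and it adds that "all participants who are randomized, even if they withdraw from the allocated treatment prior to the primary endpoints, will be included in ITT analysis". Section 5.3 has its own ITT sentence: those who consented, met eligibility (including the abstinence period before randomization) and "who receive initial dose of study medication will be included in intent to treat analyses". On continuation, 5.3 says: "Participants who are not able to comply with required periods of abstinence from marijuana use will be withdrawn from treatment".

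**The concern.** The protocol states a rule here; it is not a gap that an analysis plan would be expected to fill. One section fixes which data are analysed, and another gives investigators a free choice over the same data. The choice is made after randomization and after outcomes have been collected. It rests on a THC test whose result depends on the product assigned. If data were set aside on that basis, the groups compared would no longer be the randomized groups. Any link between failing the check and doing poorly (or well) would then carry into the treatment comparison. Section 12.1 says the trial is meant to supply effect-size and variability estimates for later studies, so a distortion would be carried forward.

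There is a second, smaller conflict. Section 5.3 withdraws such participants from treatment without discretion, whereas 10.1 leaves continuation to be judged individually.

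**Working it through.** **1. Does the clause reach randomized participants?** There are three two-week abstinence periods: screening, Cessation 1 (Visits 6-7) and Cessation 2 (Visits 13-14). Randomization follows enrollment (5.2.4), so a screening failure does not touch ITT. The other two periods come after randomization, and 10.1 applies to each period.

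**2. The rules side by side.**
- 12.0: all randomized, all available data, even after withdrawal from treatment.
- 5.3: all eligible participants given a first dose, with data up to any withdrawal of consent.
- 10.1: use of data decided individually, with no criteria and no named analysis set.

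Neither ITT sentence allows exclusion for failed abstinence after randomization. The two sentences also differ from each other (randomized versus dosed).

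**3. Who can come under the discretion?** Quantitative testing needs a positive urine screen at both ends of the cessation period, and the analyte is THC-COOH. Product THC content is in 6.2.1 and the daily limit of 1.8 g (1,800 mg) is in 5.2.7. Maximum THC supplied per day:
- High THC: 1,800 × 0.1240 = 223 mg
- THC/CBD: 1,800 × 0.07 to 1,800 × 0.09 = 126 to 162 mg
- High CBD: 1,800 × 0.0053 = 9.5 mg
- Placebo: about 0 mg

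Section 7.2 says a positive test may persist for up to three weeks, which is longer than the two-week cessation. Compliant participants on the two high-THC products can therefore enter the algorithm. A placebo participant who is negative at the start of Cessation 1 and then lapses does not meet the entry condition. Entry is not failure, however; failure needs less than 80% confidence. Stage 2 has no placebo arm, so after Cessation 2 any imbalance is among active products.

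**4. When is the decision made?** The primary CAPS-5 is at Visit 5 (5.2.9). Abstinence in Cessation 1 is judged from Visit 7, two weeks later (5.2.11). The decision therefore follows the primary outcome. It also draws on THC results, which 7.4 (writing about medical emergencies in Stage 1) says could break the blind.

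**5. Which data are exposed?** The most exposed are the Visit 7 CAPS-5, the Stage 2 outcomes and the within-subject comparison across Baseline, End of Stage 1, Stage 2 Baseline and End of Stage 2 (secondary objective 3). The Visit 5 score exists already and would be lost only if the clause were applied backwards.

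**6. Size, for illustration only.** The protocol gives no non-compliance rate, so every removal rate and correlation below is assumed. The figures describe the Stage 1 comparison if the clause were applied retroactively.
- Starting point: 12.1 states 82% power with 19 per group. With 0.4 read as Cohen's f, the noncentrality is N × f² = 76 × 0.16 = 12.16. On 3 and 72 df at 0.05, power is 82.3%, so the figure reproduces.
- Power loss: take the two high-THC arms against the other two, with the same f. Removing 2, 4 or 6 of 19 from each high-THC arm leaves N = 72, 68 or 64, and power is 79.8%, 76.5% or 72.5%.
- Bias: 20,000 simulated trials with no true effect, removing 4 of 19 from each high-THC arm. When removal has correlation 0, 0.3 or 0.5 with poor outcome, the means of those arms shift by 0.00, 0.11 or 0.17 SD. The omnibus type I error is 4.6%, 6.1% or 8.4%. With 6 of 19 removed, the shifts are 0.00, 0.15 or 0.25 SD and the error is 5.1%, 7.2% or 12.1%.

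Removal unrelated to outcome costs only power; removal related to outcome biases the comparison.

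**The case against.** The best defence is that 10.1 orders no exclusion. It names no analysis and mentions neither ITT nor CAPS-5. It could be read as covering other uses (a per-protocol set, biomarkers, the Stage 2 re-baseline) while 12.0 and 5.3 govern ITT. The statistical analysis plan, not at hand, may confine it in that way. This stands to the extent that data could be excluded, not that they will be. It does not remove the conflict, because the protocol sets no such limit.

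A reader might infer that the primary result will be biased. The documents do not support that: the Visit 5 score precedes Cessation 1, and a later lapse gives no reason to discard it.

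A reader might also infer that failures will occur almost only in arms given THC. That confuses being tested with failing. A placebo participant using outside cannabis could be positive at both time points, and prior users are eligible. What stands is unequal exposure to the discretion, inferred from the entry condition and product content. Any count of affected participants per arm would be a guess.

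On continuation, 5.3 speaks of inability to comply and of treatment, while 10.1 speaks of a laboratory classification and of the study. The two could operate in sequence, but the protocol does not say so.

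**Conclusion.** The conflict is real. As written, 10.1 permits discretionary exclusion of randomized participants' data after failed abstinence, which 12.0 and 5.3 do not allow. The discretion could fall mainly on High THC and THC/CBD, less on High CBD and least on placebo. It would be exercised after the primary assessment and with potentially unblinding results in view. Its size is unknown, and the illustrations above rest wholly on assumed rates and correlations. The risk lies chiefly with the Visit 7, Stage 2 and within-subject analyses. The text refers to study investigators, so it should not be read as discretion given specifically to site staff. Sections 5.3 and 10.1 also need to be reconciled on continuation.

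**What to change.** - In 10.1, delete *and utilization of data*. Alternatively, confine it to one predefined sensitivity analysis applied blind to arm and outcome, using the classification that 10.1 already contains (below 80% confidence is non-compliant).
- State in 12.0 that an abstinence result after randomization never removes data from the ITT analysis.
- Use one ITT definition in 5.3 and 12.0, which now differ on randomized versus dosed participants.
- Reconcile 5.3 and 10.1 on continuation after failed abstinence. The sponsor decides which applies.

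The cost is a protocol wording change and, if the second option is taken, one added sensitivity analysis. No extra data collection is needed.
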